9.1 Pre-inclusion visit

9.1.1 Verification of inclusion and non-inclusion criteria

At the time of admission of a patient in HDJ obesity, one of the investigators of the study verifies the presence of the inclusion criteria and the absence of the non-inclusion criteria in the computerized file of the patient.

9.1.2 Patient information and consent

When all the criteria allow the inclusion of the patient, the investigator informs the patient of the purpose of the study during the reception with the nurse. The investigator provides the patient with all the information described in the information note (**Appendix 5**) and, if necessary, obtains the patient's free, informed and express oral consent. This consent will be recorded in the patient's computerized medical record.

9.2 Inclusion visit

The inclusion visit takes place during the consultation with the physical therapist. The following data will be collected:

- Age, weight, height, BMI, gender (male/female);
- Adipose tissue distribution profile (visceral or subcutaneous);
- Reason for hospitalization: education, weight loss, assessment;
- History: chronic respiratory disease (COPD, Asthma, pulmonary fibrosis), diabetes, hypertension, stroke, coronary artery disease, heart surgery, heart failure, cancer under treatment, smoking (active, weaned, none), alcohol, liver cirrhosis, immunosuppression (corticosteroids, HIV, chemotherapy, other), renal failure ;
- Cardiovascular risk factors;
- Biological markers (albumin, pre-albumin, CRP, glycated hemoglobin);
- Autonomy Score (ADL Score, **Appendix 6**);
- Depression and anxiety questionnaire (HAD, **Appendix 7**).

9.3 Visit of the physiotherapist

The physical therapist visit takes place after the inclusion visit. The following measurements will be performed:

- Peripheral muscle ultrasound measurements:
 - Femoral rectus thickness;
 - Cross-sectional area of the femoral rectus;
 - Echogenicity;
 - Pennation angle.
- Grip force;
- Quadriceps FMV;
- Quality of Life Questionnaire (SF-36).

9.4 End of research visit

This visit takes place during the end-of-day consultation. It is carried out by the doctor in charge of the unit, who gives the patient the hospitalization report and ensures the transcription of the information in the research observation book.

9.5 Summary table

	Pre-inclusion	Inclusion	Visit of the physiotherapist	End of research visit
Information for the patient or family member	✓			
Collection of basic data (age, sex, BMI, medical history, etc.)		✓		
Collection of the reason for admission		✓		
Collection of information relating to medical care		✓		
GMF and handgrip			✓	
Ultrasound examination			✓	
SF - 36			✓	
Finalization of the CRF				✓

10 Statistical aspects

10.1 Calculation of the study size

Two groups of patients will be identified within our obesity patient population: a group of patients with low quality of life and a group with high quality of life. The median SF-36 quality of life score will be used to differentiate these 2 groups.

The echogenicity of the rectus femoris will be compared between these 2 groups, in order to evaluate the association between the muscular alteration of the rectus femoris by measuring echogenicity and the quality of life.

To our knowledge, no publication has evaluated the echogenicity of the rectus femoris in a population of obese patients. In the literature, an echogenicity of the rectus femoris of 120.9 ± 15.4 was found in a population of elderly patients (25). Given the presence of common pathophysiological mechanisms and similar sonographic characteristics (thickness and mCSA) in muscle damage between the elderly and obese patients, we hypothesize that the echogenicity of the rectus femoris in obese patients is similar to that in the elderly patient group with low quality of life.

In the absence of clinically relevant echogenicity difference data, we pragmatically expect a difference of at least 10 points (based on the alteration in muscle echogenicity of the resuscitation patient in 7 days (28)).

Thus, with a risk $\alpha = 0.05$ and a power of 90%, the number of subjects needed, for a two-sided test is 42 patients per group, or 84 in total.

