Primary endpoint	The primary endpoint was the association between femoral rectus muscle echogenicity and the SF-36 quality of life score.
Secondary endpoints	
The secondary evaluation criteria will be:
 
 - The association between ultrasound thickness of the femoral rectus and the SF-36 quality of life score; - The association between grip strength measured by the handgrip and the SF-36 quality of life score; - The association between quadriceps Voluntary Maximum Strength (VMS) on dynamometry and SF-36 quality of life score; - The association between quadriceps FMV with dynamometry and ultrasound measurements of the rectus femoris (thickness, echogenicity, and cross-sectional area).
Intervention	Patients will be clinically assessed for muscle function: FMV and handgrip. A muscle ultrasound and a quality of life score will also be performed in the included patients.
Number of subjects needed	84

Expected number of centers	1
Duration of the research	9 months
Statistical analysis of the data	
Statistics will be primarily descriptive and will be based on means (+/- standard deviation) or medians [minimum-maximum] depending on the distribution of quantitative variables. Qualitative variables will be described in terms of numbers and percentages. Univariate comparisons will use the usual statistical tests after verification of the distribution of the variables (Chi2 or Fisher's test, t-test, anova or their non-parametric equivalents Wilcoxon and Kruskal-Wallis tests).
 
Tests will be performed at the 5% significance level. The 95% confidence intervals will be provided for each estimate. Measures of association between categorical variables will be performed using the Chi-square or Fisher test depending on the distribution of the data. Calculations will be done using SPSS v21 IBM and R software (version 3.6.1, www.R-project.org).

Expected benefits	
This study will evaluate the association between peripheral muscle function and quality of life impairment in obese patients hospitalized in HDJ Nutrition. These results will confirm the association between muscle status and quality of life in obese patients, which is not yet clear in the scientific literature. If necessary, these results will make it possible to propose non-invasive and inexpensive tools to screen for muscle damage in this patient population. This screening could allow to propose early management programs.

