1.2.2 Peripheral muscle damage

Obese individuals have greater muscle mass and higher muscle strength than non-obese individuals. However, this increase in muscle strength is not proportional to the increase in total body mass, so that body weight-adjusted strength is lower in obese individuals than in nonobese adults (14). The increase in muscle mass in obese individuals results from the increased load imposed by body weight, which acts as a chronic stimulus to muscle tissue (15). Contrary to the benefits of resistance exercise, excess body fat does not appear to be a sufficient load stimulus to alleviate the functional consequences of obesity (difficulty walking, cycling, standing from a chair) (16).

In addition, a decrease in the specific force of the muscle is observed in obese subjects, i.e. a decrease in the force related to the sectional area. There is therefore probably a structural alteration of the muscle in the obese patient, which has not yet been well described in the literature (17). The quantity of muscle fibers decreases and is replaced by infiltration of adipose and fibrous tissue. (17). This replacement of skeletal muscle fibers decreases muscle quality and increases density, thus altering its function. The reduction in muscle mass relative to fat mass, results in a relative loss of muscle strength available to support and move body weight (17). In elderly subjects with obesity the amount of fat mass is strongly and negatively correlated with leg extension strength ($r = -0.825$) (18) with a negative impact on physical functioning and quality of life (19).

Moreover, an alteration in muscle contractile proteins coexists or occurs in a second stage in obese subjects, which can lead to muscle atrophy. Indeed, the expression of inflammation factors (IL-6 and IL-1b) by adipocytes leads to a decrease in the expression of genes coding for muscle contraction proteins, including troponin, titin and myosin (20).

The association between lower limb function, including walking ability, and health-related quality of life has been studied in young subjects with obesity, finding that a decrease in this ability correlates with impaired quality of life (13).

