1.3 Ultrasound of the peripheral muscle

Muscle ultrasound measurements have become increasingly used as a noninvasive method to determine muscle characteristics (21). Muscle characteristics, particularly muscle size and quality, have been shown to be related to muscle strength and power as well as cardiovascular performance. Ultrasound can also measure muscle echogenicity. The echogenicity of a B-mode (2D) ultrasound image is expressed by a gray scale (22). On an ultrasound image, the muscle bundles are hypoechoic areas, whereas the aponeuroses are hyperechoic. In the case of atrophied muscles, represented by hyperechoic structures, there is a decrease in the ability of ultrasound to penetrate deep into the tissue (23). Thus, the replacement of skeletal muscle fibers by fatty infiltrates decreases muscle quality and increases its density, thus increasing the echogenicity of ultrasound images (17). Muscle thickness is used to estimate the degree of atrophy (24). Ultrasound thickness of the rectus femoris has been shown to be strongly correlated with muscle cross-sectional area (mCSA) (25). More recently, mCSA has been described as strongly correlated with muscle function. Accurate assessment of mCSA may be a tool for predicting strength, muscle power, overall health, and quality of life (21). It would appear that measurement of muscle echogenicity of the rectus femoris would be more valid for assessing muscle quality. According to Wilhelm et al. (2014) there is an inverse relationship between quadriceps echogenicity and functional capacity, suggesting that the accumulation of non-contractile elements within the muscle may be a mechanism related to non-neurological muscle loss (9).

In the obese subject, ultrasound allows for improved analysis of muscle tissue by assessing the amount of muscle tissue versus non-muscle tissue (22).

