Loss of muscle strength combined with excessive body weight significantly impairs the ability to perform activities necessary for independence in daily living and proper body function (16). Choi et al (2015) showed that people with obesity, especially older individuals, are at increased risk for falls and functional decline (26). Thus, there is a decrease in exercise tolerance in subjects with obesity, the origin of which is multifactorial. The relative loss of muscle strength leads to greater fatigue during exercise and significantly limits the ability to perform the activities necessary to ensure independence in daily life (16). Peripheral muscle function requires the use of different assessment tools. Muscle capacity assessment tools, such as dynamometry or ultrasound, can be used to evaluate the different aspects of muscle function impacted by obesity (27).

2 Originality of the research

Excess body fat in obese patients appears to be responsible for muscle atrophy. This causal link is probably related to dysfunctions in adipose tissue, leading to a decrease in the expression of proteins responsible for muscle contraction (2). The recent literature highlights an alteration in quality of life, particularly in obese and elderly subjects, for which changes in muscle function would be partly responsible. In the general population of patients with obesity, especially adults and active people, this association has never been described and its mechanisms remain to be confirmed.

Changes in muscle function, and its association with impaired quality of life, can be assessed by simple, rapid and non-invasive tools. This will allow the identification of obese subjects at risk of muscle atrophy, stratify the risk, and implement prophylactic intervention or early management.

3 Research hypothesis

We hypothesize that impaired peripheral muscle function is associated with impaired quality of life in subjects with obesity.

4 Objective

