5.1 Primary endpoint

The primary end point was the association between femoral rectus muscle echogenicity and the SF-36 quality-of-life score (**Appendix 1**).

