10.2 General aspects

Statistics will be primarily descriptive and will be based on means (+/- standard deviation) or medians [minimum-maximum] depending on the distribution of quantitative variables. Qualitative variables will be described in terms of numbers and percentages. Univariate comparisons will use the usual statistical tests after verification of the distribution of the variables (Chi2 or Fisher's test, t-test, anova or their non-parametric equivalents Wilcoxon and Kruskal-Wallis tests).

The risk of low quality of life in the presence of impaired muscle function will be described by Odd-Ratios.

Tests will be performed at the 5% significance level. The 95% confidence intervals will be provided for each estimate.

Calculations will be done using SPSS v21 IBM and R software (version 3.6.1, www.R-project.org).

11 Expected results in terms of scientific and professional advances

This study will evaluate the association between peripheral muscle function and quality of life impairment in obese patients hospitalized in HDJ Nutrition.

The results of this study will confirm the association of muscle status on quality of life in obese patients, which is not yet clearly established in the scientific literature. If applicable, these results will make it possible to propose non-invasive and inexpensive predictive tools to screen for muscle damage in this patient population. This screening could make it possible to propose early management programs, such as exercise re-training or the introduction of adapted physical activity.

12 Expected benefits and risks for patients

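### Cutting SF-36 at its median for the primary test gives up about 9 to 13 points of power if its relation to echogenicity is roughly linear

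*Combined protocol and SAP*

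**What the plan says.** Section 5.1 defines the primary endpoint as an association: "The primary end point was the association between femoral rectus muscle echogenicity and the SF-36 quality-of-life score". Both measures are quantitative. Appendix 4 records echogenicity as a grey level from 0 to 255, and section 8.2 gives SF-36 sub-scores from 0 to 100.

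Section 10.1 turns this into a two-group comparison. Low and high quality of life are separated at the sample median ("The median SF-36 quality of life score will be used to differentiate these 2 groups"), and then: "The echogenicity of the rectus femoris will be compared between these 2 groups, in order to evaluate the association". The sample size rests on a 10-point difference, the published mean of 120.9 with SD 15.4, two-sided 5% and 90% power, giving 42 per group.

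On tests, section 10.2 says "Univariate comparisons will use the usual statistical tests after verification of the distribution of the variables" and names Chi2 or Fisher, t-test, ANOVA, Wilcoxon and Kruskal-Wallis, plus odds ratios for low quality of life. The synopsis names the same tests and adds: "Measures of association between categorical variables will be performed using the Chi-square or Fisher test depending on the distribution of the data". Neither lists a correlation coefficient or a regression on the continuous score.

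The fourth secondary endpoint in section 5.2 relates quadriceps strength to rectus femoris thickness, echogenicity and cross-sectional area.

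**The concern.** A median split treats a patient just below the median the same as one far below it. If quality of life changes gradually with muscle structure, that discards information already collected, and a real association is more likely to be missed. The sample median is also not a clinical threshold: it labels half the patients as low whatever their scores, and it would move in another sample.

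The rationale reads as graded. Section 1.3 reports that "there is an inverse relationship between quadriceps echogenicity and functional capacity". Section 1.2.2 cites work on walking ability "finding that a decrease in this ability correlates with impaired quality of life". The hypothesis in section 3 names no threshold: "We hypothesize that impaired peripheral muscle function is associated with impaired quality of life in subjects with obesity".

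There is a related gap in the fourth secondary endpoint. It sets one quantitative measure against three others, and the SF-36 median cannot define groups for it. No listed test applies unless one variable is cut at a point the plan does not state, so the method or the cut-off could be chosen after the data are seen.

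**Working it through.** **Inputs.** From section 10.1: difference between halves 10 points, SD 15.4, n = 84 (42 per half), two-sided alpha 0.05. The plan does not say whether 15.4 is to be read as the SD within each half or over the whole sample, so both are shown. The distribution of SF-36 and the shape of its relation to echogenicity are not given and are assumptions here.

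**The plan's own figure.** n per group = 2 × (1.960 + 1.282)² × (15.4/10)² = 2 × 10.51 × 2.372 ≈ 49.8, so 50 (51 with the t distribution), not 42. With 42 per group, power is 84.5% by the normal approximation and 83.7% by noncentral t. The shortfall from the stated 90% is therefore a separate sample-size discrepancy and is not caused by the split. What matters here is the gap between the two methods in the same 84 patients.

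**Correlation implied by 10 points.** For a linear relation and a normal SF-36 score, the halves differ by 2 × √(2/π) × r × SD_total = 1.596 × r × SD_total.

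- SD 15.4 over the whole sample: r = 10 / (1.596 × 15.4) = 0.407.
- SD 15.4 within halves: SD_total = √(15.4² + 5²) = 16.19, so r = 10 / (1.596 × 16.19) = 0.387.

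**Power of regression (Fisher z).** Power = Φ(atanh(r) × √81 − 1.960). For r = 0.387: 0.408 × 9 − 1.960 = 1.72, about 96%. For r = 0.407: 0.432 × 9 − 1.960 = 1.93, about 97%.

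**Simulation.** n = 84, 20,000 runs, every shape scaled to a 10-point difference between halves. Entries are power in %, with SD 15.4 read as within-half / whole-sample. z is the standardised SF-36 score.

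| Assumed relation | Split t-test | Linear regression | Spearman |
|---|---|---|---|
| Linear, normal score | 82.8 / 87.2 | 95.9 / 97.4 | 93.6 / 95.9 |
| Linear, uniform score | 82.4 / 86.2 | 92.5 / 95.0 | 90.9 / 93.5 |
| Linear, skewed score, beta(5,2) | 83.0 / 86.8 | 95.7 / 97.2 | 93.2 / 95.4 |
| Hockey-stick, min(z,0) | 82.3 / 86.0 | 94.9 / 96.6 | 92.4 / 94.7 |
| Step at z = −0.5 | 82.8 / 86.1 | 92.8 / 95.2 | 93.6 / 95.4 |
| Moderate S-shape, tanh(z) | 82.8 / 86.4 | 89.5 / 92.2 | 89.9 / 92.4 |
| Steep S-shape, tanh(2z) | 81.8 / 86.0 | 81.9 / 85.7 | 84.3 / 88.3 |
| Step exactly at the median | 75.8 / 79.4 | 62.7 / 67.6 | 68.0 / 72.7 |

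With no association and equal spread, all three tests rejected in 4.8–5.1% of runs. A separate simulation of 40,000 replicates gave the same picture for linear relations: normal score, split 82.7 / 86.9 against regression 95.8 / 97.5; uniform score, 82.6 / 86.6 against 92.7 / 95.1.

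**Matched gain, row by row.** Linear normal: 95.9 − 82.8 = 13.1 and 97.4 − 87.2 = 10.2 points. Linear uniform: 92.5 − 82.4 = 10.1 and 95.0 − 86.2 = 8.8. tanh(z): 6.7 and 5.8. tanh(2z): 0.1 and −0.3. Step at the median: −13.1 and −11.8.

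**In patients.** In the linear-normal case, regression reaches the split's power at 84 when n = 3 + ((1.960 + z_power) / atanh(r))². With power 0.83 and r = 0.387 this is 53.9; with power 0.87 and r = 0.407 it is 54.0. The split therefore uses 84 patients for what about 54 would give.

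**Detectable effect.** At 90% power and n = 84, r = tanh((1.960 + 1.282)/9) = 0.345, which is 8.5 points between halves (whole-sample SD) or 8.8 (within-half SD).

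**The case against.** Four objections deserve an answer.

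- **The shape is unknown.** The sources behind the graded reading concern functional capacity in older men, and walking ability in young people. Section 2 says the association has never been described in the general adult population with obesity. An inverse relationship or a correlation gives direction, not linearity. This stands, and is why the gain is stated conditionally. But nothing in the documents points to a step at the median, the one tabulated shape where the split clearly wins.
- **Regression is more sensitive to unequal spread.** With no association and residual SD assumed proportional to 0.5 + 0.5|z|, ordinary regression rejected in 15.9% of simulated trials and the split in 4.9%. With SD proportional to exp(0.3z) the figures were 8.9% and 5.1%. This is real, although the documents suggest no such pattern. Robust (HC3) standard errors brought rejection back to about 5.5% and cost under 1 point of power when spread is equal, and more when it is not. It calls for a refinement of the remedy and does not rescue the split.
- **The two-group form suits the screening aim** in sections 11 and 12.2, and the effect size was framed as a group difference. That is a reason to keep the split as a secondary presentation, not to rest the primary test on it.
- **The fourth secondary endpoint is a separate matter** of pre-specification. This is correct: none of the power figures bears on it. The same change of method closes it.

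**Conclusion.** The concern holds. The planned primary test is valid but inefficient for the question asked. If the relation is roughly linear and the plan's 10 points and SD 15.4 apply, regression in the same 84 patients has about 92–97% power against 82–87% for the split. In the linear-normal case the chance of missing a real association falls from about 13–17% to about 3–4%.

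The direction is well supported for gradual relations. The size depends on a shape and an SF-36 distribution that the documents do not give. The split-versus-regression gap does not depend on the sample-size discrepancy: taking the stated 90% at face value (implied SD about 14), regression would have about 98%. This should be changed, but it does not invalidate the trial.

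**What to change.** Pre-specify one primary analysis: linear regression of echogenicity on one SF-36 score, both continuous, reporting the slope with its 95% CI. Name that score beforehand, because section 8.2 defines only sub-scores. State Spearman correlation as the sensitivity analysis, and preferably specify robust (HC3) standard errors.

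Use the same method for thickness, grip strength and quadriceps strength against that score, and for quadriceps strength against thickness, echogenicity and cross-sectional area. Keep the median split and the odds ratios as secondary or descriptive results.

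Restate power at 84 patients with the linearity assumption declared: about 92–97% for the planned 10 points, or 90% for r of about 0.35.

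**Cost.** No extra patients or measurements. Sections 10.1 and 10.2 and the synopsis need rewriting, and the change may go to the ethics committee as a substantial modification (section 14.5). It should be settled before the data are analysed. The risk accepted is a loss of about 12–13 points of power if the truth were a step exactly at the median. The 10 points also remain a pragmatic figure: expressing them as a slope or correlation adds no clinical grounding.

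### With the stated inputs, 42 patients per group give about 84% power for a two-sided 5% test, not 90%; 42 matches the one-sided figure

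*Combined protocol and SAP*

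**What the plan says.** Section 10.1 splits the cohort at the median SF-36 score and compares mean rectus femoris echogenicity between the two halves, so the groups are of equal size. Its planning inputs are:

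- **Spread:** "an echogenicity of the rectus femoris of 120.9 ± 15.4 was found in a population of elderly patients". No other measure of variability is given.
- **Difference:** "we pragmatically expect a difference of at least 10 points".
- **Error rates:** "with a risk $\alpha = 0.05$ and a power of 90"%.
- **Result:** "a power of 90%, the number of subjects needed, for a two-sided test is 42 patients per group, or 84 in total".

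The protocol synopsis repeats the total of 84. Section 10.2 names the t-test, with the Wilcoxon test as its non-parametric alternative, and says "Tests will be performed at the 5% significance level". Neither section mentions a one-sided test, a second standard deviation, or an allowance for unusable data.

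**The concern.** The size, the power and the sidedness appear in one sentence, and the inputs just above it allow a direct check. A standardised difference of 10/15.4, about 0.65, needs roughly 50 patients per group for 90% power at the two-sided 5% level. The stated 42 is well below that.

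This is the only sample size justification in the protocol, and it concerns the primary comparison. If the power is misstated, a non-significant result will be read as stronger evidence against an association than the design supports. The plan has no visible margin to absorb the loss: the difference is described as pragmatic, the spread is borrowed from elderly patients, and nothing is added for unreadable scans or incomplete questionnaires.

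**Working it through.** **Inputs, all from section 10.1:** difference Δ = 10; SD σ = 15.4, read as a standard deviation common to both groups; α = 0.05 two-sided; power 90%; 1:1 groups.

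Standardised difference: d = 10/15.4 = 0.649.

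**Step 1. Try to reproduce 42 per group as described (two-sided).**

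n per group = 2σ²(z₁₋α/₂ + z₁₋β)²/Δ² = 2 × 237.16 × (1.960 + 1.282)²/100 = 49.8, so 50.

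The noncentral t calculation gives 50.8, so 51. Check: the t-test has 89.5% power at 50 per group and 90.1% at 51.

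The total is therefore 100 to 102. The stated 84 is 16 to 18 short and is not reproduced.

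**Step 2. Look for the setting that gives 42.**

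| Test, 5% level, 90% power | Normal formula | t-test |
|---|---|---|
| Two-sided | 49.8 → 50 | 50.8 → 51 |
| One-sided | 40.6 → 41 | 41.3 → 42 |

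The one-sided t-test gives exactly 42 per group, 84 in total.

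**Step 3. Power that 42 per group provides.**

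Standard error of the difference = 15.4 × √(2/42) = 3.361, so Δ/SE = 10/3.361 = 2.976.

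- Two-sided, normal: Φ(2.976 − 1.960) = Φ(1.016) = 84.5%.
- Two-sided, t-test: 83.7%.
- Two-sided, Wilcoxon on normal data: about 82% (simulation, 20,000 replicates).
- One-sided, for comparison: 90.8% (normal), 90.4% (t-test).

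**Step 4. Difference detectable with 90% two-sided power at 42 per group.**

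Normal: (1.960 + 1.282) × 3.361 = 10.9 points. t-test: 11.0 points.

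**Step 5. Sensitivity to the SD.** Two-sided t-test power at 42 per group, Δ = 10:

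| Common SD | Power |
|---|---|
| 13 | 94% |
| 14 | 90% |
| 15.4 (stated) | 84% |
| 16 | 81% |
| 18 | 71% |

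**The case against.** The arithmetic on the stated inputs is not in dispute. The objections concern how far the conclusion reaches.

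*A one-sided calculation is an inference.* This is correct. The match is exact for the t-test, but the one-sided normal formula gives 41, and other routes also lead to about 42: a common SD near 14, a difference near 11, or 80% power (38 to 39 per group) plus roughly 10% for unusable data. None of these is in the protocol, and each changes an input that it states. The discrepancy stands whichever route was taken.

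*The protocol never says that 15.4 applies to both groups.* Also correct. It links the elderly-patient value to the low quality-of-life group. If the other group had an SD of about 12.6, the normal formula would give (15.4² + 12.6²) × 10.51/100 = 41.6, so 42. So the size and the power conflict only if the SDs are taken as equal. But 15.4 is the only spread offered. If a second value was used, section 10.1 leaves out a decisive input and still needs correcting.

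*The true type II error is unknown.* Agreed. The protocol says it knows of no publication on this measurement in obese patients, and the SD table shows that this uncertainty can move power by more than the 6-point shortfall. The 16% is the error under the plan's own assumptions.

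*The harm is modest.* This is a one-day, minimal-risk study. The type I error is unaffected, and 84% power is above the common 80% convention. The fault is a wrong stated figure rather than an invalid design.

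**Conclusion.** The concern holds. On the only inputs that the protocol gives, 42 per group does not provide 90% power for a two-sided 5% test. It provides about 84%, or about 82% if the Wilcoxon alternative is used on normal data. The planned type II error is about 16% instead of 10%. Ninety per cent power needs 100 to 102 patients, or a true difference of about 11 points with the planned 84.

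This assumes that 15.4 is a standard deviation, that it applies to both groups, and that the median split gives equal halves. The gap of 8 to 9 per group is too large to be rounding or choice of formula, since the normal and t methods differ by only one patient per group. That 42 came from a one-sided setting is the most economical explanation, but it is unconfirmed and the conclusion does not depend on it.

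**What to change.** Correct section 10.1 in one of two ways.

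1. **Keep 84 patients and restate the power.** Suggested text: *Assuming a standard deviation of 15.4 in both groups, 84 patients (42 per group) give about 84% power to detect a 10-point difference, or 90% power to detect an 11-point difference, with a two-sided t-test at the 5% level.* This costs one sentence and no extra patients. The stated power becomes less favourable.
2. **Keep 90% power for 10 points and raise the size** to 102 (51 per group, t-test), before any allowance for unusable data. This means 18 more patients. At the pace implied by 84 patients in 9 months (9.3 per month), that is about two more months of recruitment. The total in the synopsis would change as well.

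Under either option, state the SD assumed for each group, the test and the sidedness. If 42 was derived from a second SD or a dropout allowance, give that input and its source so that the figure can be reproduced. The publication should quote the corrected power. The first option is enough to remove the error.
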